3.5.2. Exclusion Criteria

Each subject must not have any of the following conditions to be qualified to participate in this study.

- 1. Subject is currently pregnant or breastfeeding or is planning to become pregnant during the study period.
- 2. Subjects with an active infection or with a fever \geq 38.5°C (\geq 101.3°F) within 3 days of the first scheduled day of dosing
- 3. Subjects with active or symptomatic central nervous system metastases unless the metastases have been treated by surgery and/or radiation therapy and/or gamma knife, the subject has been tapered to a dose of 10 mg of prednisone (or equivalent) or less of corticosteroids for at least 2 weeks before the first dose, and the subject is neurologically stable.
- 4. Subjects with known hypersensitivity to any components of ALKS 4230

- 5. Subjects who require pharmacologic doses of corticosteroids (greater than 10 mg of prednisone daily, or equivalent); however, topical, ophthalmologic, and inhalational steroids are permitted.
- 6. Subjects with mean QT interval corrected by the Fridericia Correction Formula values of >470 msec (in females) or >450 msec (in males) at screening; subjects who are known to have congenital prolonged QT syndromes; or subjects who are on medications known to cause prolonged QT interval on ECG.
- Subjects who developed Grade ≥3 autoimmune disorders while on prior immunotherapy (e.g., pneumonitis, nephritis, neuropathy). Subjects who have immune-mediated endocrinopathies and are stable on hormone replacement therapy are not excluded. Subjects who developed autoimmune disorders of Grade ≤2 may enroll if the disorder has resolved and the subject is off systemic steroids for ≥28 days. Subjects who experienced autoimmune colitis as a toxicity of prior immunotherapy must undergo screening colonoscopy to rule out ongoing inflammation. Vitiligo is not exclusionary.
- 8. Subjects with any other concurrent uncontrolled illness, including mental illness or substance abuse, which may interfere with the ability of the subject to cooperate and participate in the study; other examples of such conditions would include unstable or poorly controlled hypertension; unstable angina; myocardial infarction, or cerebrovascular accident within 6 months of study entry; New York Heart Association Grade 3 or 4 congestive heart failure; chronic obstructive pulmonary disease or diabetes mellitus that has required 2 or more hospitalizations in the last year; severe peripheral vascular disease; or recent serious trauma.
- 9. Subjects known to be positive for human immunodeficiency virus, hepatitis B or hepatitis C, or active tuberculosis or has a known history of tuberculosis.
- 10. Subjects who are employed by Alkermes, Syneos Health, the Investigator, the study center (included permanent or temporary contract workers and designees responsible for the conduct of the study), or other affiliate of this study or is immediate family of an employee of Alkermes, Syneos Health, the Investigator, the study center, or other affiliate. Immediate family is defined as a spouse, parent, child, or sibling, whether biological or legally adopted.
- 11. Subjects with known hypersensitivity to any components of pembrolizumab (Part C subjects only)
- 12. Subjects who have had a second malignancy within the previous 3 years. This criterion does not apply to subjects with an adequately treated basal cell or squamous cell skin cancer, carcinoma in situ of the cervix, prostate cancer Gleason score <6 with undetectable prostate-specific antigen over the previous 12 months, or ductal breast carcinoma in situ with full surgical resection.

Syneos Health # 1006212

- 13. Subjects with dyspnea at rest or requiring oxygen therapy.
- 14. Subjects with active autoimmune disease requiring systemic treatment within the past 3 months or documented history of clinically severe autoimmune disease that requires systemic steroids or immunosuppressive agents.
- 15. Subjects who have received systemic immunomodulatory agents within 28 days prior to C1D1. Exceptions may be granted on a case-by-case basis by the Medical Monitor
- 16. Subjects who have received radiotherapy within the last 4 weeks before start of study treatment administration, with the exception of limited field palliative radiotherapy.
- 17. Subjects who have received administration of a live, attenuated vaccine within 4 weeks before Cycle 1 Day 1.
- 18. Prior solid organ and/or non-autologous hematopoietic stem cell or bone marrow transplant recipients.
- 19. Subjects who have received prior IL-2-based or IL-15-based cytokine therapy.

3.6. DETERMINATION OF SAMPLE SIZE

The number of subjects planned to be enrolled in this study is expected to be approximately 140 to 327. This is based on an assumption of approximately 36 to 54 subjects to be enrolled in Part A, 42 to 82 subjects to be enrolled in Part B, and up to 191 subjects to be enrolled in Part C.

Study Period	Number of Subjects		
Part A	N=36-54 (assuming 6 or 7 dose levels)		
Part B	N=42-82		
Part C new subjects	N=Up to 191		
Part C rollover subjects	Not applicable		
Part C safety run-in subjects treated at 1 $\mu g/kg/day$ dose level	N=3-6		
Total number of subjects exposed to ALKS 4230	N=140-327		

Number of Subjects Expected in Each Study Period

Note: Part C rollover subjects do not contribute the total number of subjects exposed to ALKS 4230.

In Part A of the study, the number of subjects per dose level is illustrated in Overall Study Design Schematic. The number of subjects to be enrolled in Part A will depend upon the

Version V3.0

Syneos Health # 1006212

number of dose escalations, which in turn will depend upon the safety profile of ALKS 4230. If 6 or 7 dose levels are enrolled, then the number of subjects participating in Part A is expected to be approximately 36 to 54.

Part B is designed to enroll subjects in each of 2 cohorts based on tumor type and prior therapy. The sample size of each cohort was chosen based on methodology described by Simon regarding optimal 2-stage designs for Phase 2 studies (Simon 1989). The intention in this study is to enroll cohorts that correspond to the first stage of such a design. The assumed alpha is 0.05 and power is 90%. Enrollment to these cohorts will follow a PR (unconfirmed) Simon's two-stage design enrollment as outlined in section 3.4 for Part B. Response assessments will be based on the RECIST and iRECIST guidelines.

The sample size of each cohort was chosen based on methodology described by Simon regarding optimal 2-stage designs for Phase 2 studies (Simon 1989). The intention in this study is to enroll cohorts that correspond to the first stage of such a design. The assumed alpha is 0.15 and power is 85%. Any of the following Part C cohorts may be stopped early if inadequate activity is observed:

- PD-1/L1 unapproved tumor types cohort (zero responses in the first 15 subjects)
- PD-1/L1 approved tumor types (PD-1/L1 pretreated) cohort (zero responses in the first 15 subjects)
- PD-1/L1 approved tumor types (PD-1/L1 treatment naive) cohort (≤3 objective responses in the first 20 subjects)

The Part C rollover cohort (Cohort 4) is designed to provide access to ALKS 4230 in combination with pembrolizumab for subjects initially enrolled into study Part A and Part B. It is estimated that between 0 and 54 subjects may potentially enter this cohort. Participation in the rollover cohort does not contribute to the overall number of subjects exposed to ALKS 4230. The rollover cohort will close to enrollment if the other 3 Part C cohorts have closed early due to insufficient antitumor activity. Enrollment to these cohorts will follow a partial response (unconfirmed) Simon's two-stage enrollment as outlined in section 3.4 for Part C.

3.7. TREATMENT ASSIGNMENT & BLINDING

Randomization is not planned for this open-label study.

Blinding is not applicable for this open-label study.

Syneos Health # 1006212

3.8. ADMINISTRATION OF STUDY DRUG

3.8.1. ALKS 4230 Dosing and Administration

ALKS 4230 will be administered IV as a 30-minute infusion

for 5 consecutive days, followed by a period off treatment in repeating cycles. During Cycle 1 of Parts A and B, the period off treatment will be 9 days, resulting in a cycle length of 14 days (2 weeks). Cycle 2 and subsequent cycles will have a period off treatment of 16 days, resulting in a cycle length of 21 days (3 weeks) for each cycle. Infusion for each dosing day of each cycle should begin within 2 hours (plus or minus) of the infusion start time for Day 1 of that cycle. Emergency resuscitation equipment should be available. For the first 2 treatment cycles of Part A, ALKS 4230 will be administered inpatient in a medical facility with access to medical support measures and to the intensive care unit, if needed. Subjects may be discharged on Day 6 of each of the first 2 treatment cycles may be administered on an outpatient basis. For Part B and Part C of the study, administration of ALKS 4230 may be done in an outpatient setting.

In Part C, on days where ALKS 4230 is administered in combination with pembrolizumab, ALKS 4230 should be administered as an infusion 60 (± 30) minutes after the completion of pembrolizumab infusion. For Part C, a subject's ALKS 4230 doses may be reduced by 1 dose level as needed at the discretion of the Investigator.

Sites should make every effort to target infusion timing to be as close to 30 minutes as possible. However, given the variability of infusion pumps from site to site, a window between -5 minutes and +10 minutes is permitted (i.e., infusion time is 30 minutes [-5 minutes/+10 minutes]).

ALKS 4230 may be infused using peripheral or central venous access per local standards of care and the treating investigator's judgement. All patients should have adequate intravenous access to allow the immediate management of toxicities. Subjects who do not have adequate peripheral venous access should have a central venous access device placed per local standards of care.

The amount of drug administered is based on subjects' body weight as measured at Day 1 (72 hours) of each cycle.

Sites must have written procedures in place detailing the healthcare personnel required to be on site during subject dosing, the availability of equipment and medications necessary to treat an emergency (should it occur) and the process for transferring a subject to a medical facility if necessary.

3.8.2. Pembrolizumab Dosing and Administration

Pembrolizumab is to be administered as an IV infusion over 30 minutes in a dose of 200 mg every 3 weeks, in accordance with the prescribing information (Keytruda

Version V3.0

Syneos Health # 1006212

[pembrolizumab] USPI). Subjects will be monitored for at least 1 hour for potential acute reactions to pembrolizumab prior to administration of ALKS 4230.

Sites should make every effort to target infusion timing to be as close to 30 minutes as possible for either drug. However, given the variability of infusion pumps from site to site, a window between -5 minutes and +10 minutes is permitted for ALKS 4230 and pembrolizumab (i.e., infusion time is 30 minutes [-5 minutes/+10 minutes]).

Pembrolizumab is to be obtained from the study sites' pharmacies, from commercial supplies, or provided by Sponsor in countries where pembrolizumab is not yet approved.

Version V3.0

Syneos Health # 1006212

3.9. STUDY PROCEDURES AND FLOWCHART

The schedules of visits and assessments for Part A, Part B, Part C, and Extension Phase of Part B and C can be found in section 8.2 of protocol.

Syneos Health # 1006212

4. ENDPOINTS

4.1. PRIMARY ENDPOINT

- The incidence of DLTs from the first dose through the end of the DLT observation period (Part A)
- The incidence and severity of treatment-emergent AEs according to the National Cancer Institute (NCI) Common Terminology Criteria for Adverse Events (CTCAE) version 4.03 or higher (Parts A, B, and C)
- ORR based on Response Evaluation Criteria in Solid Tumors (RECIST) guidelines version 1.1 (Eisenhauer et al 2009) (Part B and Part C)

4.2. SECONDARY ENDPOINTS

- Serum concentrations of ALKS 4230 and descriptive PK parameters
- Presence of anti-ALKS 4230 antibodies in serum
- Immune (i-) ORR (iORR) based on Immune RECIST (iRECIST) guidelines (Seymour et al 2017)
- Disease control rate (DCR) based on RECIST guidelines and immune DCR (iDCR) based on iRECIST guidelines
- DOR based on RECIST guidelines and immune DOR (iDOR) based on iRECIST guidelines
- DRR for Part B and Part C Cohorts C5, C6, C7 only
- Progression-free Survival (PFS) and immune PFS (iPFS) for Part B and Part C Cohorts C5, C6, C7 only
- Numbers of circulating CD8 T cells, Tregs, and NK cells in peripheral blood
- Serum concentrations of IL-6 and other cytokines

4.3. EXPLORATORY ENDPOINTS

Syneos Health # 1006212

4.4. ANTITUMOR ACTIVITY ENDPOINTS

- Objective response rate (ORR) based on Response Evaluation Criteria in Solid Tumors (RECIST) guidelines version 1.1 and Immune (i-) ORR (iORR) based on Immune RECIST (iRECIST) guidelines (Seymour et al 2017)
- Disease control rate (DCR) based on RECIST guidelines and immune DCR (iDCR) based on iRECIST guidelines
- Duration of response (DOR) based on RECIST guidelines and immune DOR (iDOR) based on iRECIST guidelines
- Progression-free Survival (PFS) based on RECIST and immune PFS (iPFS) based on iRECIST for Part B and Part C Cohorts C5, C6, C7 only
- Time to response (TTR) based on RECIST guidelines and immune TTR (iTTR) based on iRECIST guidelines

4.5. SAFETY ENDPOINTS

Safety will be assessed using the following:

- DLTs
- Treatment-emergent adverse events (TEAEs)
- Laboratory Evaluations (hematology, coagulation, chemistry, urinalysis tests)
- Vital Signs (systolic and diastolic blood pressure, pulse, respiratory rate, and oral body temperature)
- ECG parameters (overall assessment; heart rate; RR, PR, QRS, and QTc intervals)
- ECOG Performance Status

4.6. TISSUE BIOMARKERS ENDPOINTS

Collection of fresh tumor samples via biopsy is optional during the study. Subjects with accessible tumors who are willing to undergo biopsy should provide samples at baseline and while on treatment around C2D8. A punch biopsy is preferred for tissue collection from melanoma patients.
Alkermes Protocol # ALK4230-A101

Version V3.0

Syneos Health # 1006212

These samples will be analyzed by immunohistochemistry and/or immunofluorescence for markers of immune activation. They can also be used for gene expression analysis using method such as NanoString. The tissue biomarker data will be presented in data listings and done separately for PART A, B and C respectively.

Syneos Health # 1006212

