# 6.3. Exploratory Objectives

• To describe changes in post-treatment subject blood and/or tumor tissue samples as compared with baseline/pretreatment samples (Part B)

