#### 14.4.6. Tissue Biomarker Analysis

The baseline values, post-treatment values, and the changes in density of TILs, ratio of cytotoxic TILs, immunosuppressive TILs, and density of signals of immune-cell-mediated killing will be summarized.

The correlation between antitumor efficacy endpoints (best overall response, progression free survival) and baseline status (or values) for endpoints derived from tumor tissues will be estimated. The efficacy endpoints will be summarized separately based on baseline status, or low and high values.

The correlation between antitumor efficacy endpoints (best overall response, progression free survival) and the change from baseline in post-treatment for endpoints derived from tumor tissues will be estimated.

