2. PURPOSE

The purpose of this statistical analysis plan (SAP) is to ensure that the summary tables, data listings and figures (TLFs) which will be produced, and the statistical methodologies that will be used, are complete and appropriate to allow valid conclusions regarding the study objectives described in the latest study protocol.

2.1. **RESPONSIBILITIES**

Syneos Health will perform the statistical analyses and is responsible for the production and quality control of tables, figures and listings (TLFs) detailed in this SAP text/Mock tables for safety and anti-tumor endpoints.

Alkermes will be responsible for pharmacokinetic (PK), blood-related pharmacodynamics and immunogenicity analyses and reporting. Syneos will be responsible for tumor-related pharmacodynamics (PD) listing.

STDM and ADaM data files for tumor-related PD datasets that contain tissue biomarker end points will be produced by Syneos Health. Only STDM data files for PC, blood-related PD, and ADA datasets will be produced by Syneos Health. All the PK, ADA and bloodrelated PD analyses will be specified in a separate analysis plan.

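### The SAP gives only data listings for tissue biomarkers, although protocol 14.4.6 commits to summaries and correlations, and SAP 11 does not declare the reduction.

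*SAP*

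**What the plan says.** **Protocol.** Section 6.3 sets the exploratory objective: "To describe changes in post-treatment subject blood and/or tumor tissue samples as compared with baseline/pretreatment samples (Part B"). SAP 3.3 carries it forward almost unchanged. Protocol 14.4.6 (Tissue Biomarker Analysis) then states what is to be done with the tissue data. Its first sentence, beginning "The baseline values, post-treatment values, and the changes in density of TILs", commits to summaries of these and the other named tissue measures: TIL ratios, immunosuppressive TILs and signals of immune-mediated killing. It goes on to commit to estimating "The correlation between antitumor efficacy endpoints (best overall response, progression free survival) and baseline status (or values) for endpoints derived from tumor tissues", to tabulating efficacy by baseline level, and to correlating the same two efficacy endpoints with change from baseline.

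**SAP.** Section 4.6 describes the optional biopsies at baseline and around C2D8 and the assays, and ends: "The tissue biomarker data will be presented in data listings and done separately for PART A, B and C respectively". Section 2.1 (Responsibilities) agrees: "Syneos will be responsible for tumor-related pharmacodynamics (PD) listing". The same section plans the underlying data: "STDM and ADaM data files for tumor-related PD datasets that contain tissue biomarker end points will be produced by Syneos Health". It also defines the scope of the companion document: "All the PK, ADA and bloodrelated PD analyses will be specified in a separate analysis plan". Section 11, which records changes from the protocol's analysis, has three entries: durable response rate, irRC/iRECIST, and an added PFS analysis in ovarian subjects.

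**The concern.** The protocol promises group-level description and association. The SAP prescribes a different and smaller output, and does not record the difference in the section kept for that purpose. This is an explicit SAP rule that conflicts with an explicit protocol rule, not merely a missing detail.

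Two things are at stake, both modest. First, Part B has an exploratory objective about change in tumor tissue, and subjects are asked to consider an invasive optional biopsy before and during treatment to serve it. Under the SAP, the report would print each subject's values but give no typical baseline, on-treatment or change value. Second, protocol 14.4.6 leaves the boundary between low and high values and the correlation method unspecified, and protocol 14.2 leaves further detail to the SAP. The SAP supplies none. In an open-label trial with interim data cuts, those choices would then be made with outcome data to hand.

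**Working it through.** No sample size, power or event count bears on this point, so the check is a comparison of texts.

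**Step 1. Carry each protocol commitment across.**

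| Commitment in protocol 14.4.6 | In the SAP? | Declared in SAP 11? |
|---|---|---|
| (a) Summaries of baseline, post-treatment and change values | No; listings | No |
| (b) Correlation of best overall response and PFS with baseline values | No | No |
| (c) Efficacy summarized by baseline status or by low against high value | No | No |
| (d) Correlation of best overall response and PFS with change | No | No |

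Count: 4 commitments, 0 carried forward, 0 of the 4 omissions declared.

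**Step 2. Is the work placed elsewhere?** The separate plan named in SAP 2.1 covers pharmacokinetics, anti-drug antibodies and blood-based pharmacodynamics. The sponsor's own reporting role in that section has the same limits. Tumor tissue is in neither. SAP Sections 8 and 9 contain no tissue-biomarker analysis, and the Pharmacodynamic Population (SAP 5.4) and the handling rules in SAP 6.7 lead to no tissue summary.

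**Step 3. Is it plausibly a deliberate reduction?** SAP 4.6 follows protocol 12.3.2.1 closely on sampling and assays. Where the protocol goes on to compare on-treatment with baseline results and to use baseline tissue for correlative work, the SAP has the listings sentence. The SAP glossary still defines TIL and tumor microenvironment, though no SAP analysis uses them. This suggests that the analyses were taken out, but the SAP gives no reason.

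**Step 4. Does SAP 11 normally record such a change?** Yes. Two of its three entries, durable response rate and irRC/iRECIST, are analyses dropped from the protocol.

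**Step 5. What remains?** Individual listings remain, and so do the planned analysis datasets. Protocol 14.4.6 still names the tissue measures, the efficacy endpoints and the predictors (baseline and change). The blood part of the exploratory objective goes to the separate plan. What is missing is any group summary of tissue data, the cut-points and the correlation method.

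**The case against.** The strongest reply is that this is a documentation mismatch on optional, exploratory data. Paired biopsies may be few, and with a handful of subjects a listing may be as informative as a table. The objective asks only for description, says blood and/or tissue, and covers Part B only. The correlations with response and PFS come from 14.4.6 and are no part of that objective. The table templates are in a separate document (SAP 15), the exploratory endpoint lists show no text and may be redacted, and SAP 2.1 divides work between vendor and sponsor, so a vendor listing does not exclude analysis by someone else.

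Much of this stands, and it keeps the point small. It does not remove it. Sparse data could justify listings, but the SAP does not say so, and the argument does not reach the baseline correlations, which need no paired sample. Under protocol 12.3.2.2, Part B and Part C subjects must agree to provide archival tissue if available, also for correlative use. The templates cannot be checked here; a summary table among them would contradict SAP 4.6, which would still need correcting. Planning an analysis dataset is compatible with analysis elsewhere, but no document assigns that analysis to anyone.

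A reader might go further and infer that the objective cannot be answered at all, or that any later tissue analysis would be wholly post hoc. The documents support neither. Listings of baseline and on-treatment values show individual change, which is weak description but still description. An analysis that followed 14.4.6 would rest on measures and endpoints named in advance; only the cut-points and the method would be open.

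**Conclusion.** The point holds as a minor inconsistency. The SAP replaces all four tissue-biomarker analyses in protocol 14.4.6 with listings, places none of them elsewhere, and does not declare the change. The tumor-tissue part of the Part B exploratory objective therefore has individual listings but no planned summary.

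Four of four is a count of text items, not a measure of effect on the trial. It should not be read as proof that the sponsor has cancelled the analyses: the protocol commitment still stands, and the documents do not show what was intended. No primary or secondary endpoint, sample size or decision rule depends on it.

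The conclusion assumes that the redacted or separate material (exploratory endpoint lists, table templates) holds no overriding statement. If it does, SAP 4.6 and 2.1 still need to be brought into line with it.

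**What to change.** 1. In SAP 4.6, restore the descriptive summaries of protocol 14.4.6: n, mean, SD, median and range of the baseline value, the on-treatment value (about C2D8) and the paired change, for each named tissue endpoint, at least for Part B. These are the statistics that protocol 14.2 already plans for continuous variables. No test is needed.
2. Restore the summary of efficacy by baseline tissue value and the correlations with best overall response and PFS where numbers allow. State the low/high cut-point rule and the correlation method before the analysis is run. Judge feasibility separately: the change correlations depend on the number of paired samples; the baseline correlations do not.
3. In SAP 11, declare and justify any 14.4.6 analysis that is not done. If listings only is the considered choice, a short entry giving the reason would resolve the contradiction, though the tissue part of the objective would still have no summary.

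The cost is a few extra exploratory tables on what may be a small optional-biopsy subset, drawn from the ADaM data that SAP 2.1 already plans. The results will be imprecise and should be labelled exploratory.
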